- If the heparin infusion was 1401 to 1700 units per hour then 30 mg of protamine will be given.
- If the heparin infusion was 1701 to 2000 units per hour then 35 mg of protamine will be given.
- If the heparin infusion was 2001 to 2300 units per hour prior then 40 mg of protamine will be given.
- If the heparin infusion was 2301 to 2600 units per hour then 45 mg of protamine will be given.
- If the heparin infusion was greater than 2600 units per hour then 50 mg of protamine will be given.

Adherence will be measured in hours UFH is not being infused (unless infusion is stopped per institutional guidelines, such as a supratherapeutic anti-Xa UFH level) according to the inpatient electronic medical record.

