Further data collected will include information regarding standard of care therapy (collected daily during duration of study), demographics (collected following study enrollment and screening), and medical information (collected following study enrollment and screening). Regarding standard of care therapy, data collected will consist of whether or not intravenous fluids were given; whether or not antibiotics were administered, number of antibiotics received, and class of antibiotics given (penicillin, cephalosporin, macrolide, fluoroquinolone, vancomycin, other); whether or not supplemental oxygen was received with documentation of need for noninvasive positive pressure ventilation or mechanical ventilation; whether or not pain medication was provided, including type of pain medication (opioid, NSAIDs, acetaminophen, other); number of red blood cell transfusions given; and whether or not exchange transfusion was necessary. Demographics include age, race, and sex. SCD related medical information includes number of previous episodes of ACS, current administration of outpatient hydroxyurea, and prior DVT or PE. General medical information includes history of myocardial infarction; chronic lung disease, defined as a documented baseline arterial oxygen saturation less than 90% and/or home supplemental oxygen requirement; previous stroke; and current or former smoker.

Prespecified feasibility criteria are as follows: the ability to enroll potential study participants, which includes the timely notification of hospitalized patients with ACS, the capacity to consent eligible individuals, and the ability to appropriately randomize screened patients within 24 hours of diagnosis, all of which should occur at a frequency greater than or equal to 80%; inclusion and exclusion criteria that does not exclude potential study participants at a frequency greater than or equal to 20%; the proper administration of the study drug at a frequency greater than or equal to 90%; and the ability to completely and accurately collect clinical data of interest at frequency greater than or equal to 90%. The final aim of our pilot study is to provide preliminary data, with respect to treatment effect and variance, for future sample size calculations given the lack of existing data to help guide this process.

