
Potential adverse events include heparin-associated risks, such as allergic reaction, major bleeding, minor bleeding, thrombocytopenia, and heparin induced thrombocytopenia (HIT), or any other adverse reaction suspected secondary to drug administration. All subjects enrolled in the study and received any UFH will be included in the safety evaluation.

A member of the research staff will collect the study data. All data required by the study protocol will be documented in the inpatient electronic medical record system. De-identified subject information will be written on Case Report Forms (CRFs) and all data collected will be stored in locked files at the Hemophilia Center of Western Pennsylvania (HCWP). Additionally, data will be entered into research electronic capture (REDCap) and compared to ensure consistency. No personal identifiers will be associated with the data. The Institutional Review Board (IRB) may inspect records at any time.

A sample size of 20 subjects for the pilot study is based on clinical rather than statistical considerations and should provide a preliminary estimate of primary and secondary clinical outcomes and assess prespecified feasibility criteria as detailed above. Based on 75,000 to 100,000 African Americans with SCD in the United States who develop ACS at a frequency of 8.8 per 100 patient years, with 50% developing ACS at some point during his or her lifetime, and given the fact that approximately 30 patients are admitted annually at UPMC hospitals (Presbyterian, Montefiore, Magee, Shadyside) with ACS, we estimate that at least 80%, or 24 patients per year, will meet inclusion and exclusion criteria, and expect to enroll 10 patients, or slightly less than 50% per year, which should meet the n=20 subjects required for the pilot study.^{3,4} This is a pilot feasibility study, so comparisons will be descriptive, including frequencies and percentages for categorical variables and mean, median, range, and standard deviation for continuous variables.

Demographics and medical information will be summarized with descriptive statistics as well. Adverse events will be summarized by frequency, relatedness, and severity.

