Subjects will be considered enrolled in the study after informed consent is obtained. Each study participant will receive a unique subject identification number. Afterwards, screening assessment will be completed by a member of the research staff. All individuals will have any reason for study exclusion documented. Following enrollment and screening, patients will undergo randomization. Prior to beginning the study, an independent statistician will perform a 1:1 randomization using randomization software ensuring 10 patients are placed in each arm of the study. A card will be labeled heparin or standard of care, placed in a sealed envelope numbered 1 to 20, and stored in locked files at HCWP. Following enrollment and screening, a member of the research staff will access the appropriate numbered envelope to ascertain patient assignment.

Study participants will be free to withdraw at any time by notifying a member of the research staff. Any data collected prior to the time of withdrawal will continue to be used, but no additional information will be collected. Processed blood sample results will continue to be used; however, remaining samples will be destroyed or used as indicated by the subject. The reason and date of study withdrawal for all subjects will be recorded.

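### Feasibility targets are judged on bare percentages with no interval; if drug administration is scored per patient, 9/10 meets the 90% target with an exact 95% CI of 55.5% to 99.7%

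*Combined protocol and SAP*

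**What the plan says.** Feasibility for a phase III trial is the stated purpose of the pilot (section 1.0). Section 3.3 gives each criterion one numeric target:

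- Notification, consent and randomization within 24 hours: "all of which should occur at a frequency greater than or equal to 80" percent.
- Eligibility criteria: exclusions must stay below 20%.
- Heparin: "the proper administration of the study drug at a frequency greater than or equal to 90" percent.
- Data: "the ability to completely and accurately collect clinical data of interest at frequency greater than or equal to 90" percent.

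On sample size, 3.3 states: "A sample size of 20 subjects for the pilot study is based on clinical rather than statistical considerations". It adds that this number "should provide a preliminary estimate of primary and secondary clinical outcomes and assess prespecified feasibility criteria as detailed above". On analysis, it states that "comparisons will be descriptive, including frequencies and percentages for categorical variables and mean, median, range, and standard deviation for continuous variables".

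Section 4.2 describes 1:1 allocation "ensuring 10 patients are placed in each arm of the study", so 10 patients are assigned heparin. Section 3.1 gives the only measure of administration: "Adherence will be measured in hours UFH is not being infused". Table 1 records adherence on each of Days 1 to 7. No section converts hours into a yes/no for proper administration, gives a denominator for any criterion, mentions an interval, or says what follows if a target is missed.

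**The concern.** The feasibility results are the main product of this trial, and some of them may rest on 10 or 20 patients. A percentage compared with a target, with nothing beside it, does not show how little such numbers can establish. A report that drug was properly given in 90% of patients, criterion met, could come from a process that works much less often than that. Those planning the phase III trial would have no statement of that uncertainty in front of them. The plan also leaves open what is being counted, so the denominator could be settled after the data are seen.

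**Working it through.** **The plan's own figures.** The sample size has no statistical inputs, so there is no formula to reproduce. The accrual arithmetic in 3.3 is consistent: 30 × 0.80 = 24 eligible per year; 10/24 = 41.7% enrolled; 20/10 = 2 years.

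**Inputs.** Targets of 90% and 80% (3.3); 10 patients assigned heparin (4.2); 20 patients in all (3.3). Assumptions, because the documents do not say: drug administration and data completeness are each scored yes/no per patient, and patients are independent. The true rates used below are illustrative.

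**Drug administration, n = 10.** The target is met at 9 or 10 successes. With true rate p, P(met) = 10p⁹(1 − p) + p¹⁰.

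- p = 0.70: 0.1211 + 0.0282 = 0.149
- p = 0.80: 0.2684 + 0.1074 = 0.376
- p = 0.90: 0.3874 + 0.3487 = 0.736

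The exact (Clopper-Pearson) 95% interval for 9/10 has a lower limit L that solves 10L⁹(1 − L) + L¹⁰ = 0.025, giving L = 0.555. Its upper limit U solves 1 − U¹⁰ = 0.025, giving U = 0.975^(1/10) = 0.997. The interval is 55.5% to 99.7%. For 10/10 it is 69.2% to 100%.

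**Data completeness, n = 20.** The target is met at 18 or more. P(met) is 0.036 at p = 0.70, 0.206 at p = 0.80 and 0.677 at p = 0.90. The exact interval for 18/20 is 68.3% to 98.8%; for 20/20 it is 83.2% to 100%.

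So no possible result, even a perfect one, puts the lower 95% limit at 90% with 10 or 20 patients.

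**Criteria with larger denominators (80% target).** If accrual runs as forecast for two years, about 30 × 2 = 60 patients are admitted and 24 × 2 = 48 are eligible.

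| Denominator | Successes needed | Exact 95% CI at that count | P(met) at a true 70% |
|---|---|---|---|
| 60 | 48 | 67.7% to 89.2% | 5.7% |
| 48 | 39 | 67.4% to 91.1% | 5.7% |
| 20 | 16 | 56.3% to 94.3% | 23.8% |

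The last row matters for randomization within 24 hours. That criterion is counted on screened patients, and 4.2 places screening after consent, so its denominator may be nearer 20 than 60.

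**If the unit is the day.** Ten patients over 7 days give at most 70 patient-days, and the 90% target needs 63. If days were independent, a true 80% would meet the target 2.0% of the time. Days within a patient are not independent, so the real figure would lie roughly between 2% and 38%. The result depends heavily on a unit that the plan does not state.

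**The case against.** The strongest objection is that the 9-of-10 rule is not in the protocol. Section 3.1 measures adherence in hours, and 3.3 does not say whether data completeness is counted per patient or per item. If hours or days are the unit, the 38% and 15% figures do not apply. This stands, and those figures are given here only under the stated assumption. It also shows why the unit must be named.

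A second objection is that this is openly a descriptive pilot and anyone can compute an interval from a count. That is true, and nothing here asks for a larger sample or a hypothesis test. An exact interval is itself descriptive, and planning it costs nothing.

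Three stronger readings are tempting, but the documents do not support them:

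- *That feasibility as a whole lets a poor process through more than a third of the time.* The 38% belongs to one criterion, at one assumed true rate, under per-patient scoring.
- *That a process truly at 90% missing the target 26% of the time (1 − 0.736) is a small-sample defect.* A process exactly on a cut misses it often at any size: 32% at n = 20, 42% at n = 100 and 47% at n = 1000.
- *That one patient reverses the phase III decision.* Section 3.3 gives targets but no stop/go rule, and nothing bars amending a procedure and proceeding.

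A reader might also want a middle zone, for example amend and proceed at 7 or 8 of 10. That cuts the chance of calling a true 90% process infeasible to 1.3%. It leaves the 38% unchanged, because the upper cut does not move. The chance of proceeding becomes P(X ≥ 7): 65.0% at a true 70% (14.9% under the 9-of-10 cut) and 38.2% at a true 60% (4.6% under that cut). This is a trade-off for the sponsor to weigh, not a correction.

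**Conclusion.** The point holds as a gap in reporting and definition, not as an error in the sample size. The plan compares feasibility percentages with targets, gives no measure of precision, and does not say what is counted. Under per-patient scoring, meeting the 90% drug target at 9/10 is compatible with true rates from 55.5% to 99.7%, and meeting the 90% data target at 18/20 with 68.3% to 98.8%. A true 80% drug process would meet its target 38% of the time, and a true 70% process 15%. These figures rest on yes/no scoring of 10 and 20 independent patients, which the documents do not state. Criteria with denominators of about 48 to 60 are less affected. Severity is low: this is an improvement at no cost that limits what the pilot can claim.

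**What to change.** Add a short paragraph to 3.3 and keep the stated targets:

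1. For each feasibility criterion, state the scoring unit and define the numerator and denominator. For drug administration, say how the hours recorded under 3.1 become proper administration. For data, say whether completeness is per patient or per item.
2. Report each proportion with its numerator, denominator and exact (Clopper-Pearson) 95% CI. Where the unit is hours, days or data items, use an interval that allows for clustering within patient.
3. Describe a criterion that reaches its target as *target met by the point estimate*, with the interval shown, and not as established.

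Three zones (go, amend, not feasible) remain an option for the sponsor, with the trade-off shown above; they are not part of the required change.

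The cost is one paragraph, with no extra patients or data. The downside is that the reported intervals will be wide.

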This is a single-center, randomized controlled, open-label, pilot study to determine the feasibility of performing a larger multicenter phase III trial to assess the effects of unfractionated heparin (UFH) in acute chest syndrome (ACS). Adult patients with sickle cell disease (HbSS, SC, or S β^0) aged 18 years or older admitted to the University of Pittsburgh Medical Center (Presbyterian, Montefiore, Magee, Shadyside) hospitals with a diagnosis of ACS will be eligible for screening to participate in the trial. Subjects meeting inclusion and exclusion criteria and consenting to study will be randomized within 24 hours of diagnosis to one of two treatment arms, Arm A, anticoagulation and standard of care, or Arm B, no anticoagulation and standard of care. Weight-adjusted UFH will be given at doses of 80 units per kilogram followed by 18 units per kilogram per hour intravenously for 7 days, or until discharge, if discharge is shorter than 7 days. UFH will be monitored by standard protocol to maintain the anti-Xa UFH level in the therapeutic range per institutional guidelines. Standard of care will include intravenous fluids, antibiotics, supplemental oxygen, incentive spirometry, pain medication, red blood cell transfusions, and exchange transfusion. Prespecified feasibility criteria consists of the ability to enroll potential study participants, which includes the timely notification of hospitalized patients with ACS, the capacity to consent eligible individuals, and the ability to appropriately randomize screened patients within 24 hours of diagnosis. Additional feasibility objectives involve ensuring appropriate inclusion and exclusion criteria, proper administration of the study drug, and the ability to completely and accurately collect clinical data of interest. The final aim of our pilot study is to provide preliminary data, with respect to treatment effect and variance, to allow sample size calculation in a larger trial given the lack of data available to help guide this process. All clinical outcomes, except the number of red blood cell transfusions administered, will be defined as beginning with randomization and measured in hours. The primary clinical outcome is duration of hospitalization. Secondary clinical outcomes include the duration of hypoxemia, duration of fever, duration of leukocytosis, duration of moderate to severe pain, total dose of opioids, and the number of red blood cell transfusions administered. Additional clinical outcomes will include the rate of transfer to the intensive care unit, requirement for mechanical ventilation, and development of multiorgan dysfunction syndrome. Further data collected will include demographics and medical information. A sample size of 20 subjects for the pilot study is based on clinical rather than statistical considerations and should provide a preliminary estimate of primary and secondary clinical outcomes and assess prespecified feasibility criteria as detailed above. This is a pilot feasibility study, so comparisons will be descriptive, including frequencies and percentages for categorical variables and mean, median, range, and standard deviation for continuous variables.

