The primary clinical outcome is duration of hospitalization. Secondary clinical outcomes include the duration of hypoxemia, duration of fever, duration of leukocytosis, duration of moderate to severe pain, total dose of opioids, and the number of red blood cell transfusions administered. Additional clinical outcomes will include the rate of transfer to the ICU, requirement for mechanical ventilation, and development of MODS.

Duration of hospitalization will be defined as beginning with randomization and measured in hours. Conclusion of hospitalization will be defined as the time of order entry into the inpatient electronic medical record system stating the patient is appropriate for medical discharge, per the discretion of the treating physician. Duration of hypoxemia will be defined as beginning with randomization and measured in hours. Hypoxemia will be defined as arterial oxygen saturation less than 90% according to pulse oximetry and/or the continued need for supplemental oxygen. If the patient's baseline arterial oxygen saturation is less than 90%, hypoxemia will be defined as a decrease in arterial oxygen saturation below the patient's baseline. Similarly, if

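### Ten patients per arm cannot give a treatment effect precise enough to size phase III, and the planned summaries include no interval that would show this

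*Combined protocol and SAP*

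**What the plan says.** Section 3.3 gives the last aim of the pilot as "to provide preliminary data, with respect to treatment effect and variance, for future sample size calculations". The opening summary says the same and names the use: "with respect to treatment effect and variance, to allow sample size calculation in a larger trial". Sections 1.0 and 2.1 repeat the aim. The reason given is that little existing data is available to guide the calculation.

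On size, section 3.3 states "A sample size of 20 subjects for the pilot study is based on clinical rather than statistical considerations". Section 4.2 has an independent statistician "perform a 1:1 randomization using randomization software ensuring 10 patients are placed in each arm of the study". The primary clinical outcome is continuous: "Duration of hospitalization will be defined as beginning with randomization and measured in hours".

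On reporting, section 3.3 says "comparisons will be descriptive, including frequencies and percentages for categorical variables and mean, median, range, and standard deviation for continuous variables". The document contains no confidence interval, standard error, target difference or rule for turning pilot results into a phase III sample size.

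**The concern.** A sample size needs two main inputs for a continuous outcome: the difference to detect and the SD. The aim asks the pilot for both. The required number varies with the inverse square of the difference, so an imprecise difference does far more damage than a moderately imprecise SD.

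If the phase III team took the pilot's observed difference as its target, a chance-large difference would give a trial that is too small. A chance-small one would give a trial far larger than needed, and a wrong-sign one would give no usable number. A table of means, medians, ranges and SDs, without an interval for the difference, would not warn a reader of this.

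**Working it through.** **Inputs from the documents.** 10 per arm (section 4.2); a continuous primary outcome in hours (section 3.3); descriptive summaries only (section 3.3). The total of 20 has no alpha, power, effect or SD behind it, so no power formula can reproduce it.

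**Assumptions, not in the documents.** Roughly normal data, equal SDs, no dropout; phase III at two-sided 5% and 80% power; true standardized effect d between 0.2 and 1.0. Positive d means that heparin is better.

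**Precision of the difference.** The 95% half-width is t(0.975, 18 df) × SD × √(2/10) = 2.101 × 0.447 × SD = 0.94 SD.

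**Precision of the pooled SD.** The 95% limits are the estimate times √(18/χ²). With χ² quantiles 31.53 and 8.23 on 18 df, the factors are 0.76 and 1.48. The required number scales with the square, so its factors are 0.57 and 2.19.

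**Chance of the wrong sign.** Φ(−d/√0.2) is 33% at d = 0.2, 25% at 0.3, 13% at 0.5 and 4% at 0.8.

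**Number needed in phase III.** n per arm = 2 × (1.960 + 0.842)²/d² = 15.70/d². At d = 0.5 this is 15.70/0.25 = 62.8, so 63.

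**Sizing on the observed effect.** Pilots of 10 versus 10 were simulated (at least 200,000 per setting). Each right-sign pilot was used to size phase III from its observed d, and the true power of that trial was then found.

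| True d | Power below 80%, right-sign pilots | Median true power, right-sign pilots | Proceeds with power below 80%, all pilots |
|---|---|---|---|
| 0.2 | 75% | 29% | 50% |
| 0.3 | 67% | 46% | 50% |
| 0.5 | 58% | 68% | 50% |
| 0.8 | 52% | 77% | 50% |
| 1.0 | 50% | 81% | 49% |

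At d = 0.5, the planned n per arm among right-sign pilots has a 10th to 90th percentile range of about 12 to 660, against 63 needed. True power is below 50% in 37% of them, and about 12% would plan more than 500 per arm.

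**Sensitivity.** Planning for 90% power changes the shares falling short of the planned power very little. With lognormal data, the share of right-sign pilots giving power below 80% is 72%, 65% and 62% at d = 0.3, 0.5 and 0.8.

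**Using only the SD.** With the target difference fixed in advance at 0.5 SD, sizing on the raw pilot SD gives power below 80% in about 53% to 55% of cases, but below 50% in only about 4%. Median power is 78%.

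**The case against.** The documents call the data preliminary, say openly that the size is "based on clinical rather than statistical considerations", and describe all comparisons as descriptive. They never say that phase III will be sized on the raw observed effect. They give no phase III alpha, power or target, and their only numerical success criteria are feasibility frequencies. All of this stands, and it makes the simulation a picture of one possible use of the data. It does not answer the point that the treatment effect is named four times as an input to sizing and that no other source for it is named.

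A reader might go further and infer that phase III would usually be underpowered. The documents do not support that. It holds only if phase III is sized on the observed effect, goes ahead after a favorable pilot, and the true effect is small to moderate. Over all pilots the figure is about 50%, and it is also about 50% at d = 1.0 after a favorable pilot. A reader might also infer that phase III would be abandoned after a wrong-sign result, but the plan has no go or no-go rule on the effect.

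Nor does the whole aim fail. The variance is half of it, and an SD on 18 degrees of freedom is a rough but usable input.

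Finally, a normal-theory interval for a mean difference could be worked out from the reported means, SDs and arm sizes, and printing it would reveal the imprecision without curing it. That also stands, so the intervals are the smaller part of the remedy.

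**Conclusion.** The point holds for the treatment-effect half of the aim. The ±0.94 SD half-width depends only on 10 per arm and approximate normality. An interval that wide cannot separate a large benefit from none, and a sizing input that gives anything from about 12 to 660 per arm when 63 are needed is not usable.

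The power and sign percentages are illustrative. They rest on the assumptions listed above and on a plug-in rule that the plan does not state. Hospital stay in hours is probably skewed, so they should not be read as exact. Dropout would make the precision worse.

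The feasibility purpose and the conduct of the pilot are unaffected. This is a matter of what the pilot can claim and how it reports its results, and it should be corrected.

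**What to change.** 1. Reword the final aim in the opening summary and in sections 1.0, 2.1 and 3.3. The pilot should supply the SD, event rates and process rates for phase III planning. State that the phase III target difference will be set by clinical importance and not by the difference observed in the pilot.
2. In section 3.3, add 95% confidence intervals for between-arm differences and for the SD to the descriptive tables.
3. Optionally, note that phase III planning should allow for uncertainty in the SD (95% limits 0.76 to 1.48 times the estimate), for example by using an upper confidence limit. The choice of limit belongs in the phase III protocol. As one example, the one-sided 80% upper limit is √(18/12.86) = 1.18 times the estimate. For a fixed difference it raises the planned number by 1.18² ≈ 1.4 times, and it lowers the chance of missing 80% power from about 53–55% to about 19–20%.

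Items 1 and 2 cost a few sentences and some extra table columns, with no added patients, visits or procedures. The cost of item 3 would fall on phase III.
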